		
 
• Bleeding requiring intravenous vasoactive drugs
 
 
Type 3c:
 
 
• Intracranial hemorrhage (does not include microbleeds or hemorrhagic transformation; does include intraspinal); subcategories confirmed by autopsy, imaging, or lumbar puncture
 
• Intraocular bleed compromising vision
 
 
Type 4: Coronary artery bypass-related bleeding; not applicable.
 
Type 5: Fatal bleeding is bleeding that directly causes death with no other explainable cause. The site of fatal bleeding is specified as intracranial, gastrointestinal, retroperitoneal, pulmonary, pericardial, genitourinary, or other. BARC fatal bleeding is categorized as either definite or probable as follows:
 
Type 5a:
 
Probable fatal bleeding (type 5a) is bleeding that is clinically suspicious as the cause of death, but the bleeding is not directly observed and there is no autopsy or confirmatory imaging.
 
Type 5b:
 
Definite fatal bleeding (type 5b) is bleeding that is directly observed (by either clinical specimen such as blood, emesis, stool or imaging) or confirmed on autopsy.

Clinical Success		Absence of bleeding in a Target Lesion after embolization with the Lava LES and any adjunctive devices employed during the index procedure, without the need for emergency surgery, re-embolization, or other target territory reinterventions within 30 days of the index procedure.
Device-Related Events		
Device-related events constitute those events that are deemed directly attributable to the Lava LES itself.
 
Catheter entrapment will be considered a device-related adverse event, as will rebleeding after the index procedure. Continued bleeding, i.e. failure of the Lava LES to arrest hemorrhage, will constitute failure of the effectiveness endpoint but is not an adverse event, in and of itself.
 
An event that is related to a prior device-related event is also considered to be device-related.

Hemorrhage	Bleeding	Bleeding is defined with respect to the Investigator-assigned

Category	Term	Definition
		target territories. Bleeding outside of a target territory is not tabulated in the primary or secondary endpoints, except for access site bleeding which is not tabulated in the primary endpoint but is included in the secondary access-site endpoints.

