The objective of Lava LES embolotherapy is to occlude feeding vessels to bleeding target lesions. Clinical Success, the primary effectiveness endpoint, averaged approximated 80% in the 51 publications that reported the endpoint. This rate was consistent with the expected outcomes reported in the Society of Interventional Radiology document. An 8% margin was used to assign the effectiveness performance goal of 72%.

The study is powered for the primary effectiveness endpoint of Clinical Success. Based upon a one-sided exact binomial test using a significance level of 0.025, the literature-derived performance goal of 72%, and an anticipated observed success rate of 84%, the required sample size to achieve a level of 80% power is 101 Target Lesions. Assuming a 10% attrition rate through 30 days, a total of 113 subjects will need to be enrolled.

 The anticipated Clinical Success rate of 84% was estimated after discussions with the Sponsor's scientific advisors.

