### 3.3 POPULATIONS FOR ANALYSES

The intention to treat (ITT) dataset, defined as all consented subjects in whom the Lava LES study device entered the vasculature irrespective of adherence with the entry criteria, treatment received, subsequent withdrawal, or deviation from the protocol, will be used for all safety endpoints. Each safety-related endpoint will be assessed on a subject-level basis; expressed as the number of subjects

experiencing at least one event divided by the number of subjects with evaluable observations (see 3.4.1 handling of missing data).

The complete cases (CC) dataset, defined as all ITT subjects who complete 30-day follow-up, will be used for all effectiveness endpoints. Categorical effectiveness endpoints will be expressed as the number of Target Lesions meeting the effectiveness criteria divided by the number Target Lesions with evaluable observations (completed 30-day follow-up). Certain effectiveness endpoints will be assessed on a lesion-level basis; for example, the primary effectiveness endpoint of Clinical Success. Other effectiveness endpoints will be assessed at the subject level; for example, measures related to resource utilization including procedure duration, contrast volume administered, and fluoroscopy time.

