### **Handling of Missing Data**

All attempts will be made to limit the amount of missing data. For all analyses of the primary endpoints, the number of observations available will be reported so the reader can assess the impact of missing data. In general, and for the primary endpoint analyses, missing data will not be imputed and analyses will be based on available data. For missing values on the primary safety endpoint, an adjustment to the denominator will be made based on the amount of evaluable data. For each visit (or reporting time point), the occurrence rate will be calculated as the number of subjects with certain endpoint occurrence term over the number of evaluable subjects. The evaluable subjects at each reporting time point include all subjects who are enrolled by the snapshot date and

- 1) had an endpoint occurrence within (on or before) the reporting cutoff days (30 days), or
- 2) had a follow-up at or after the lower limit of the reporting window (23 days), or
- 3) the withdrawal consent date/recorded lost-to-follow-up date at or after the lower limit of the reporting window.

Sensitivity analyses will be performed to assess the impact of missing data and potential correlation in the data for the primary endpoints. Three different sensitivity analysis are planned: (1) As described in the protocol, Target Lesions with unavailable effectiveness data will be assumed to have missing data at random and will be imputed by random selection with replacement of data from Target Lesions with complete data. (2) A tipping point analysis will be conducted in which lesions or subjects censored without an event prior to 30 days follow-up are sequentially imputed as failures at the time of censoring. (3) A generalized estimating equation (GEE) logistic regression model will be used to estimate clinical success taking into account potential correlation of multiple Target Lesions within a subject using an exchangeable working correlation structure. The analyses for all the secondary endpoints will not include imputation for missing data, and no formal statistical hypotheses will be tested.

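### Subjects who die before day 23 without a safety event, qualifying bleed or reintervention leave both primary denominators, and no planned analysis shows the result with those deaths named and counted as failures

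*SAP*

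**What the plan says.** **Safety.** SAP 3.4.1 (Handling of Missing Data) adjusts the denominator to evaluable subjects and gives three ways in: an endpoint event by day 30; that the subject "had a follow-up at or after the lower limit of the reporting window (23 days"; or a withdrawal or loss-to-follow-up date at or after day 23. Protocol 7.7 has the same idea with two routes, an MAE or follow-up to the lower window limit. Neither mentions death.

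**Effectiveness.** SAP 3.3 states: "The complete cases (CC) dataset, defined as all ITT subjects who complete 30-day follow-up, will be used for all effectiveness endpoints". Protocol 6.6.3 uses the same core definition and adds subjects who fail the effectiveness endpoint before the 30-day timepoint, however short their follow-up. SAP 3.3 omits that addition.

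**Missing data.** The SAP does not impute for the primary analyses. Its first sensitivity analysis assumes missing at random and resamples from lesions with complete data. Its second is a tipping point that turns censored lesions or subjects into failures one after another. The third, a GEE model, concerns correlation between lesions, not missingness.

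**Deaths that count as events.** Protocol Section 18 makes death from target-territory ischemia or infarction an MAE. BARC Type 5 ("Fatal bleeding is bleeding that directly causes death with no other explainable cause") is an effectiveness failure, and its Type 5a covers suspected fatal bleeding without direct observation, autopsy or imaging. All-cause and bleeding-related 30-day mortality are secondary endpoints (SAP Section 2).

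**The concern.** In a hemorrhage trial, death within 30 days is an outcome, and there is little reason to think that it is unrelated to how the treatment went. If event-free early deaths leave the denominator, each primary rate describes subjects seen to day 23 or beyond, plus those who had an event. The safety rate is nominally an ITT rate, so a reader may take it to cover everyone treated. Study success rests on two exact lower limits with little room to spare, so a handful of excluded deaths can decide whether a limit falls above or below its goal. If the handling is not settled in advance, it will be argued over once the deaths are known.

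**Working it through.** **1. Reproduce the plan's sample size.** Inputs from SAP 3.2: "Based upon a one-sided exact binomial test using a significance level of 0.025"; "the required sample size to achieve a level of 80% power is 101 Target Lesions"; goal 72%; anticipated success 84%; 10% attrition. Rule: take the smallest r with P(X ≥ r | n, p0) ≤ 0.025; power is P(X ≥ r | n, p1).

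- Effectiveness, n = 101, p0 = 0.72, p1 = 0.84: r = 82, actual alpha 0.0227, power 81.9%.
- Attrition: 101 / 0.90 = 112.2, rounded up to 113.
- Safety (Protocol Synopsis: goal 82%, anticipated 92%), n = 101: r = 91, actual alpha 0.0181, power 81.6%.

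The plan's figures reproduce.

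**2. Trace a death before day 23 through the rules.**

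| What preceded or caused death | Safety rate | Effectiveness rate |
|---|---|---|
| MAE | in, as failure | depends on the bleeding and reintervention record |
| Target-lesion BARC 3 or greater bleed (including Type 5a/5b), or reintervention | out, unless also an MAE | in as failure (Protocol 6.6.3); out if SAP 3.3 is read literally |
| None of these | out | out |

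The last row is the gap common to both endpoints.

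**3. Effect on the success test.** The documents give no mortality figure, so this is an assumption: 113 treated subjects with one lesion each, 6 such deaths (6/113 = 5.3%), no other losses, and the planned success rates among the other 107. Then 0.84 × 107 = 89.9, taken as 90, and 0.92 × 107 = 98.4, taken as 98. The exact one-sided 97.5% lower limit is the 0.025 quantile of Beta(x, n − x + 1).

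| Endpoint (goal) | Deaths excluded, as planned | Deaths counted as failures |
|---|---|---|
| Effectiveness (72%) | 90/107 = 84.1%, limit 75.8%: above | 90/113 = 79.6%, limit 71.0%: below |
| Safety (82%) | 98/107 = 91.6%, limit 84.6%: above | 98/113 = 86.7%, limit 79.1%: below |

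**4. How many deaths it takes.** Over 113, the limit clears the goal at 91/113 (72.02%) for effectiveness and 101/113 (82.2%) for safety. With the planned rates among the rest:

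- Safety still clears with 3 deaths counted as failures (101/113), but not with 4 (100/113, limit 81.1%).
- Effectiveness still clears with 5 (91/113), but not with 6 (90/113).

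At the far end, suppose 11 deaths (11/113 = 9.7%, about the whole attrition allowance). Then 83/102 and 92/102 are enough to pass as written. Over all 113 they are 73.5% and 81.4%, with limits 64.3% and 73.0%.

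**5. Check the obvious remedy.** Suppose death is added to the evaluable rule and nothing else changes. An event-free death then counts as free of MAE. A result of 95/107 (limit 81.2%) misses the goal; adding 6 event-free deaths gives 101/113 (limit 82.2%), which meets it. That edit alone can turn a failing safety result into a pass.

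**The case against.** The strongest reply is that the deaths-as-failures result is largely planned already. The tipping point covers lesions or subjects censored without an event before 30 days, which on a natural reading includes an event-free death, and Protocol 7.7 says that it spans every possible imputation outcome. Its last step, with 6 deaths and no other losses, is the 90/113 above. Mortality is also reported, with exact 95% intervals (SAP 3.4.3). This stands in part. A reader might infer that early deaths are ignored or hidden throughout, and the documents do not support that. What remains is that the tipping point never names death, does not separate deaths from losses, and does not enter the success rule.

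A reader might also infer that a death counts against the device only if it is fatal bleeding or part of an MAE. That is too strong. Any target-lesion BARC 3 or greater bleed, emergency surgery, re-embolization or other target-lesion reintervention before death is already an effectiveness failure, whatever the later cause of death.

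Two further objections hold and limit the claim:

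- The goals contain no all-cause mortality term. The 82% was built from ischemia, non-target embolization and three device events (Protocol 7.8.1). The 72% is an 80% literature average for Clinical Success less 8 points, with 30-day mortality tabulated separately. Falling below a goal with all deaths as failures is therefore a bound, not a failed test of the planned hypothesis.
- The number of deaths is assumed, and 6 is exactly where effectiveness crosses. Inclusion requires life expectancy above 30 days, which should keep the count down, though it does not say how a death is scored.

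**Conclusion.** The point holds in a limited form. Both primary rates omit subjects who die before day 23 with no MAE, no qualifying target-lesion bleed and no reintervention. No strategy for these deaths is stated by name, and the one analysis likely to include them blends them with losses to follow-up. At the planned success rates, counting 4 such deaths as failures brings the safety limit below its goal, and 6 does so for effectiveness. Those counts assume one lesion per subject, 113 treated and no other losses. The documents do not show that deaths on this scale will occur, and they do not make a deaths-as-failures result the proper primary test. A related defect needs no assumption: SAP 3.3 and Protocol 6.6.3 define Completed Cases differently. Read literally, the SAP drops even a subject who rebleeds and then dies before the visit. This is worth correcting before analysis, but it does not invalidate the design.

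**What to change.** Keep both primary analyses and make these changes to the SAP:

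1. For each primary endpoint, pre-specify a named supportive analysis over all treated subjects (safety) or their Target Lesions (effectiveness) in which every death by day 30 counts as a failure. Say how losses without death are handled in it; treating them as in the primary analysis keeps the two questions apart.
2. Report it beside the primary result, with the number of deaths excluded from each primary denominator, and keep it separate from the loss-to-follow-up tipping point.
3. State that it is a bounding analysis, because the 72% and 82% goals were derived without an all-cause mortality term.
4. Do not add death to the evaluable rule on its own, for the reason shown in step 5 of the working.
5. Restore in SAP 3.3 the Protocol 6.6.3 clause that keeps early effectiveness failures in Completed Cases.

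The cost is SAP wording and two table rows; the data are already collected. The downside for the sponsor is a less favourable supportive estimate next to each primary result.

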### 7.2 Primary Safety Endpoint

The primary safety endpoint is the 30-day rate of MAE, defined by the occurrence of any one of the following events between enrollment and 30 days after the index procedure:

1. Ischemia or infarction of the target territory;
2. Non-target embolization;
3. Allergic reactions to Lava;
4. Catheter breakage;
5. Catheter entrapment.

See **Section 5.1**, above, for a complete description of the elements of the primary safety endpoint.

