More generally, in the case of partial adverse event onset date or date of death, the unknown portion of the date of the event will be imputed. If the month and year are known, the 1st of the month will be used for analysis. If only the year is known, the event will be analyzed as if it occurred on June 30th of the known year. In the rare case that the date is fully unknown, the date will be imputed as the initial treatment date. Imputation of partial dates is subject to the condition that it

must occur on or after the initial treatment date. In the case where the imputed date is prior to the initial treatment date, the date of the initial treatment will be used. As death cannot occur before any documented subject contact, for date of death the imputed date of death must occur on or after last known contact in study.

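### The SAP's June 30 rule for year-only event dates can place a true 30-day event outside the window, depending on the calendar month of the procedure

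*SAP*

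**What the plan says.** SAP 3.4.1 (Handling of Missing Data) ends with a date convention: "in the case of partial adverse event onset date or date of death, the unknown portion of the date of the event will be imputed". It has three cases.

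- Month and year known: "If the month and year are known, the 1st of the month will be used for analysis".
- Year only: "If only the year is known, the event will be analyzed as if it occurred on June 30th of the known year".
- Nothing known: "In the rare case that the date is fully unknown, the date will be imputed as the initial treatment date".

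Two bounds follow. The general one is "In the case where the imputed date is prior to the initial treatment date, the date of the initial treatment will be used". The one for deaths is that "for date of death the imputed date of death must occur on or after last known contact in study". Both can only move a date later. No upper bound is given at last contact, study exit or day 30.

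The endpoints are 30-day endpoints. Protocol 7.2 counts a major adverse event (MAE) if it occurs "between enrollment and 30 days after the index procedure". The evaluability rules in SAP 3.4.1 include a subject who "had an endpoint occurrence within (on or before) the reporting cutoff days (30 days), or". They also keep a subject without such an event who was followed to day 23 or later, or whose withdrawal or loss to follow-up is dated day 23 or later.

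Earlier in the same section, the SAP says that missing data are not imputed for the primary endpoint analyses, and that secondary endpoint analyses do not include imputation.

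**The concern.** The month-known rule picks the earliest day of the month, and the fully-unknown rule picks day 0. Neither can push a true in-window adverse event past day 30. The year-only rule can, because June 30 is a mid-year placeholder with no relation to a 30-day window. The planned 30-day visit closes at day 37 (Protocol 8.5), so for many index dates June 30 falls after any planned contact with the subject.

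Two oddities follow. Knowing the year of an adverse event can remove it, although it would count if nothing were known about its date. And the same incomplete record is treated differently for a March procedure and an August one. SAP 1.1 expects 12 months of enrollment, so index dates in the affected months are likely.

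If the rule is applied to endpoint events, those exposed are mainly MAEs, BARC Type 3 or greater rebleeding without reintervention, and the 30-day mortality and serious adverse event secondary endpoints. The planned tipping-point analysis re-imputes only lesions or subjects censored without an event before 30 days. It would not restore a misdated event in a subject followed to day 30 or beyond.

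**Working it through.** **The plan's own figures.** The date rule has no stated figure. The surrounding ones reproduce. With an exact binomial test of 72% against 84% at one-sided 0.025, the smallest N with at least 80% power is 101 (success at 82 or more; alpha 0.0227, power 0.819). 101/0.9 = 112.2, rounded up to 113. The Wilson lower limit for 91/101 is 82.7%, as in SAP Table 1.

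**Imputed study day.** From SAP 3.4.1, for an adverse event with a year-only date:

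imputed date = later of (June 30 of the known year, treatment date); study day = imputed date − index date; counted if study day ≤ 30.

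For an event in the same calendar year as the index procedure (365-day year):

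| Index date | Days in year | Imputed study day | Counted? |
|---|---|---|---|
| Jan 1 to May 30 | 31+28+31+30+30 = 150 | 31 or later | No |
| May 31 to Jun 30 | 31 | 0 to 30 | Yes |
| Jul 1 to Dec 31 | 184 | 0 (treatment-date floor) | Yes |

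150/365 = 41.1%. Examples: index May 30 gives day 31; March 1 gives day 121; January 15 gives day 166. For deaths the last-contact bound can move the date later still.

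**Crossing the year end.** Day 30 falls in the next year for index dates December 2 to 31. If the event is known only to the next year, it goes to June 30 of that year. An index date of December 15, 2020 with an event known only as 2021 gives day 197. Index December 2 has 1 of its 31 possible event days (0 to 30) in the next year, and December 31 has 30 of 31. The sum is 1+2+…+30 = 465 combinations, equivalent to 465/31 = 15 index days.

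**Overall share.** Assume index dates uniform over the year, event days uniform over 0 to 30, and only the year known. The share of true in-window events moved out is (150+15)/365 = 45.2%. This is conditional on a year-only date; the documents give no frequency for such dates.

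**Same check on the other rules.** The month-known rule, applied to every index date and every event day 0 to 30, moves none out. The fully-unknown rule puts an adverse event at day 0, so it moves none out either.

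**Effect of one event.** Exact one-sided 97.5% lower limits:

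| Endpoint and goal | One short | Lower limit | At threshold | Lower limit |
|---|---|---|---|---|
| Safety 82%, n = 101 | 90 | 81.3% (fails) | 91 | 82.5% (passes) |
| Safety 82%, n = 113 | 100 | 81.1% (fails) | 101 | 82.2% (passes) |
| Effectiveness 72%, n = 101 | 81 | 71.1% (fails) | 82 | 72.2% (passes) |

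A safety subject whose only event is pushed out becomes a success if followed to day 23 or later. If the subject meets none of the evaluability conditions, the subject leaves the denominator instead: 90/101 becomes 90/100 (lower limit 82.4%), and 100/113 becomes 100/112 (82.03%). At these boundaries either route turns a fail into a pass.

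**The case against.** **Reach.** The strongest objection is that the SAP says primary endpoint data are not imputed, so the date convention may not touch them. This stands as an ambiguity, not as an exemption. The convention comes later under the same heading, is introduced as applying more generally, and covers onset and death dates without excluding MAEs, rebleeding or deaths. A reader might infer that the plan as written removes events from a primary endpoint. The documents do not settle that.

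**Exposure.** Much of both endpoints lies outside the rule or carries its own date. Protocol 10.2 does not treat reinterventions as adverse events, and Protocol 18 says the same of continued bleeding, so the rule does not date them. Four of the five MAE components arise from delivering Lava or from the delivery catheter, and are in essence tied to the procedure date. The fifth, ischemia or infarction, requires an intervention or death, which normally leaves a dated record. This stands and narrows the exposure.

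**Likelihood.** Follow-up is short, both primary endpoints are CEC-adjudicated (Protocol 5.1, 5.2), and source verification is 100% (Protocol 16). A committee deciding whether an event fell within 30 days would hardly rely on a placeholder date. This stands too, although the SAP does not say that CEC timing prevails. The realistic opening is an event after discharge, first learned of at a 30-day contact that may be by telephone (Protocol 8.5).

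**Direction.** A reader might infer that the error always favours success. It does not. For index dates July 1 to December 31, a same-year, year-only adverse event goes to day 0, so one that truly occurred after day 30 would count as a failure.

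**Conclusion.** The point holds as a minor defect in a stated rule. For index dates January 1 to May 30, and for late-year procedures with an event known only to the next year, a year-only date puts a true day 0-30 event after day 30. An adverse event with no date information is counted. Under the uniform assumptions, about 45% of true in-window events with a year-only date would be moved out.

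Such dates should be very rare, so the expected effect is small. The documents give no frequency from which to quantify it. The possible consequence is a changed result at the boundary. That is true of any single event in a binomial test; what is specific here is that the calendar month of the procedure would decide it.

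The safety margin should be read at the right size. The 101 in the sample size section is a Target Lesion count for effectiveness. Safety is assessed on intention-to-treat subjects, with 113 planned: if all are evaluable, 12 MAEs are compatible with success (101/113), against 10 at 101 evaluable subjects.

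The conclusion on the primary endpoints depends on the date convention being applied to them, which the SAP leaves open. Sample size and power are unaffected.

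**What to change.** In SAP 3.4.1, replace June 30 by the earliest date in the known year that is on or after the index procedure and, for deaths, also on or after last contact. This follows the logic of the other two rules. The imputed date then never falls after the true date, so no true in-window event is lost.

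Add one sentence stating whether the date convention applies to the primary and secondary endpoints, and that CEC-adjudicated timing governs the 30-day primary endpoints when it is available.

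The cost is two sentences, with no change to sample size or data collection. There is a small downside: a true post-day-30 event with a year-only date may be counted as a failure, and any descriptive time-to-event summary would use a somewhat early date. For a test against a performance goal, that error is conservative.
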